1.3.6.3 APX005M

1.3.6.3.1 Clinical Pharmacology Summary of APX005M

APX005M is an IgG1 humanized mAb with the S267E mutation at the Fc region. APX005M binds with high affinity to human CD40 ($K_d = 1.2 \times 10^{-10}$ M) and monkey CD40 ($K_d = 3.5 \times 10^{-10}$ M), but does not cross-react with mouse or rat CD40. APX005M blocks the binding of CD40 to CD40L. The APX005M binding epitope has been mapped to 2 specific regions on CD40. These are 92TSEACESCVLHRSCSP107 and 125PCPVGFFSNVSSAFEKCHP144. The region 92TSEACESCVLHRSCSP107 is known as a CD40L binding domain. It has been shown that CD40L-blocking antibodies tend to have more potent CD40 agonistic activities than CD40L-non-blocking antibodies [73].

The direct cytotoxicity effect and the antibody effector functions such as Antibody-dependent cellular phagocytosis (ADCP) of APX005M were determined in CD40 positive human lymphoma xenograft models in mice. In human lymphoma Ramos models, APX005M was capable of inhibiting tumor growth in a dose-dependent manner, and eradicated established tumors at 3 mg/kg and 10 mg/kg. A significant anti-tumor effect was also observed in the rituximab-resistant Namalwa model [64]. These data suggest that APX005M, as a single agent, can induce potent growth inhibition of CD40-expressing human tumors.

Preliminary human data shows that APX005M induces a dose-dependent activation of APCs (as demonstrated by increases in expression of activation markers such as CD54, CD70, CD80, CD86, HLA-DR), T cell activation and increases in circulating levels of IL12, INF- γ , TNF- α and IL6.

1.3.6.3.2 Pharmacokinetics of APX005M

Nonclinical pharmacokinetics (PK) of APX005M were determined in a Good Laboratory Practice (GLP) repeat-dose toxicology study using cynomolgus monkeys. Weekly intravenous (IV) administration of 5 doses of APX005M was well tolerated at 0.3, 3, and 30 mg/kg. The PK properties of APX005M are typical of other mAbs and comprise low clearance (average range of 0.401–7.27 mL/h/kg), small volume of distribution (average range of 57–80.1 mL/kg), and long terminal half-life (average >66 hours at 3 mg/kg and 30 mg/kg). Positive anti-drug antibodies (ADA) titers were observed in all animals in the low-dose group (0.3 mg/kg) but not in the high-dose group (30 mg/kg) [16]. Based on these results, the no observed adverse effect level (NOAEL) was considered 30 mg/kg.

There are limited human PK data with APX005M at this time. Exposures to APX005M at dose levels of 0.03 mg/kg or less were for the most part below the limit of quantitation (BLOQ). IV administration of APX005M at doses between 0.1 and 1 mg/kg lead to rapid increase in serum concentrations, reaching a maximum just after the end of the infusion. Levels declined rapidly thereafter and were for the most part BLOQ between 24 and 168 hours after the start of dosing.

Increases in the dose of APX005M (0.1 mg/kg to 1 mg/kg) led to approximately dose-proportional increases in maximum serum concentration (Cmax) and area under the curve at the last measurable time point (AUC_{0-t}). No accumulation of APX005M was observed with every 21 days dosing.

1.3.6.3.3 Safety Summary of APX005M

Study APX005M-001 is a first in human phase 1 dose escalation study of APX005M with 8 pre-planned dose levels. APX005M was administered to study subjects at doses up to 1 mg/kg. At the 1 mg/kg dose level, 1 out of 6 dose limiting toxicity (DLT)-evaluable subjects experienced a DLT (grade 4 cytokine release syndrome). Two additional subjects at the 1mg/kg dose level experienced serious adverse events (SAE) in later cycles (Grade 3 cytokine release syndrome and Grade 4 thrombocytopenia). On May 2, 2016 Apexigen decided to discontinue dose escalation and enroll up to 6 subjects in dose level 0.6 mg/kg (originally designed as an intermediate de-escalation dose level) and an additional 3 subjects at the previously completed dose level 0.3 mg/kg to better characterize the safety and pharmacodynamics (PDn) of APX005M and to help establish the single agent recommended phase 2 dose (RP2D). The RP2D for APX005M as a single agent every 21 days is 0.3 mg/kg body weight.

As of the data cutoff date of 14 April 2017, 432 AEs have been reported in the 30 subjects enrolled in Study APX005M-001. The majority of AEs (371/432 [85.9%]) were mild or moderate (\leq Grade 2) in severity, 44 events (10.2%) were reported as Grade 3, and 8 events (1.9%) were reported as Grade 4. No Grade 5 events have been reported.

As of 14 August 2017, 17 SAEs had been reported in 6 subjects. With the exception of cytokine release syndrome and thrombocytopenia, all SAEs were considered unrelated to APX005M. Cytokine release syndrome is an expected on-target side effect of CD40 agonists. No thromboembolic or bleeding events have been reported to date for APX005M.

APX005M demonstrated a dose-dependent activation of APCs (as demonstrated by increases in expression of activation markers such as CD54, CD70, CD80, CD86, HLA-DR), T cell activation and increases in circulating levels of IL12, INF- γ , TNF- α and IL6.

For further details on the APX005M-001 study please refer to latest version of the APX005M Investigator's Brochure [64].

Symptoms associated with cytokine release syndrome (including but not limited to flushing, itchiness, chills, fever, rash, tachycardia, hypotension, hypertension, rigor, and myalgia) after administration of APX005M are possible and have been observed in some of the subjects receiving APX005M. Guidance for monitoring and management of cytokine release syndrome are included in this protocol and in the APX005M Investigator's Brochure.

Transient transaminase elevations (\leq Grade 2) have been observed in several subjects with liver metastases, which were not associated with a particular dose of APX005M. Six subjects with

liver metastases enrolled in the study experienced a transient increase in total bilirubin. Liver function test abnormalities tend to resolve to baseline within 7 days from APX005M administration.

Transient decreases in peripheral blood lymphocyte count in general and B-cell count in particular have been observed for APX005M as well as for other CD40-agonistic mAbs and are believed to be a PDn effect. Transient decreases in platelet counts were observed for some of the subjects receiving higher doses of APX005M but were not associated with bleeding or other clinical manifestations.

Other symptoms might also occur, including allergic reactions, which could be severe, pulmonary edema, and rarely, thromboembolic events, myocardial infarction and/or death. In the ongoing Phase 1 study APX005M-001, APX005M demonstrated a dose-dependent activation of APCs, T cell activation and increases in circulating levels of cytokines.

The biological effects and the overall tolerability of APX005M up to 1mg/kg body weight suggest a best in class profile for APX005M and the possibility of a safe and tolerable combination with other immunomodulatory antibodies such as nivolumab.

1.4 Clinical Experience Involving Serum Enzyme Elevations

The safety and preliminary efficacy of cabiralizumab is currently being evaluated in 3 clinical trials. A common feature observed across the clinical trials is an elevation of AST, CK, and LDH after the administration of cabiralizumab. These alterations are the consequence of the direct effect of anti-CSF1R antibodies on the Kupffer cell in the liver that results in a depletion of these cells. Depletion of Kupffer cells allows the enzymes, which are released following normally occurring liver cell turnover, to enter circulation (where they are measured by routine laboratory assessment) rather than being absorbed by the Kupffer cells. Elevated liver enzymes, thus, represent a PD marker rather than a safety signal. The observed elevations were asymptomatic not permanent and not associated with clinical sequelae. Similar effects have been observed across other CSF1R targeted agents (see cabiralizumab IB for additional details). There is a significant body of evidence from the cabiralizumab preclinical and clinical experience as well as from others in the field that suggest elevations of serum enzymes caused by inhibition of the CSF1R pathway are reversible and are not associated with clinical sequelae [66, 74-78].

1.4.1 Serum Enzyme Elevations with Cabiralizumab

In Study FPA008-003, 34 subjects have been dosed as part of Phase 1a dose escalation (24 in cabiralizumab monotherapy and 10 in cabiralizumab + nivolumab combination therapy) and 195 subjects have been dosed as part of Phase 1b dose expansion as of 1 August 2017. In Phase 1a, CK was elevated in 11 of 34 subjects (32%), and 3 events (1%) were Grade 3 or higher. AST was elevated in 16 of 34 subjects (47%), and 10 events (29%) were Grade 3 or higher. ALT was elevated in 4 of 34 subjects (17%), and none of these were Grade 3 or higher. In Phase 1b, CK was elevated in 82 of 195 subjects (42%), and 29 events (15%) were Grade 3 or higher. AST was elevated in 76 of 195 subjects (39%), and 14 events (7%) were Grade 3 or higher. ALT was

elevated in 39 of 195 subjects (20%), and five events (3%) were Grade 3 or higher. The serum enzyme elevations for Studies FPA008-001 and FPA008-002 follow a similar pattern.

Please refer to the cabiralizumab IB for more detailed information about these serum enzyme elevations.

1.4.2 Serum Enzyme Elevations with Nivolumab

The hepatic enzyme changes caused by cabiralizumab and nivolumab are due to different mechanisms that should not be additive. For cabiralizumab, the elevations are hypothesized to be due to the on-target effect of Kupffer cell reduction and not to liver cell toxicity. Hepatic AEs, including possible drug induced liver injury (DILI) cases, have been manageable using an established management algorithm and thus do not meaningfully alter the benefit/risk of nivolumab in the advanced malignancy populations. Guidelines for management and safety assessments focused on the liver can be found in Section 4.8 and Section 4.9.

1.4.3 Serum Enzyme Elevations in APX005M

Transient transaminase elevations (\leq Grade 2) with APX005M administration have been observed in several subjects with liver metastases, which were not associated with a particular dose of APX005M. Six subjects with liver metastases enrolled in the study experienced a transient increase in total bilirubin. Liver function test abnormalities tend to resolve to baseline within 7 days from APX005M administration. Elevations of ALT, AST, CK, and LDH were not associated with signs or symptoms of hepatic or muscle injury as demonstrated by concurrent normal total bilirubin, INR, aldolase, and troponin levels.

Please refer to the APX005M Investigator's Brochure for more detailed information about serum liver enzyme elevations and their management, as outlined in Section 4.8 and Section 4.9. Additional laboratory abnormality management algorithms are included to help manage elevations of CK in Section 4.8 and Section 4.9.

2. Objectives

2.1 Phase 1a Objectives

2.1.1 Primary

- To assess the safety and tolerability of APX005M in combination with cabiralizumab
- To assess the safety and tolerability of APX005M in combination with cabiralizumab and nivolumab
- To determine the recommended RP2D of APX005M in combination with a fixed dose of cabiralizumab and nivolumab in advanced melanoma, NSCLC, and RCC

2.1.2 Secondary

- To determine the AE profile of this combination

2.1.3 Exploratory

- To characterize the pharmacokinetic (PK) profile of APX005M when administered in combination with cabiralizumab and nivolumab
- To characterize the pharmacodynamic (PD) profile of APX005M when administered in combination with cabiralizumab and nivolumab
- To further characterize the PD profile and immunogenicity of APX005M in combination with cabiralizumab and nivolumab by analyses of pre-treatment and on-treatment tumor biopsies and blood collection

2.2 Phase 1b Objectives

2.2.1 Primary

- To determine the objective response rate (ORR) using RECIST v1.1 to APX005M in combination with cabiralizumab and nivolumab in 3 separate patient cohorts: advanced melanoma, NSCLC, and RCC whose tumors are resistant to anti-PD-1/PD-L1 therapy
- To evaluate the safety and tolerability of the RP2D of APX005M in combination with cabiralizumab and nivolumab

2.2.2 Secondary

- To determine the PFS of patients with melanoma, NSCLC or RCC treated with APX005M in combination with cabiralizumab and nivolumab whose tumors are resistant to anti-PD-1/PD-L1 therapy.
- To determine the OS of patients with melanoma, NSCLC or RCC treated with APX005M in combination with cabiralizumab and nivolumab whose tumors are resistant to anti-PD-1/PD-L1 therapy.
- To assess the association of selected biomarker measures and clinical efficacy measures using pre-treatment and on-treatment tumor biopsies and blood collection

2.2.3 Exploratory

- To identify immune correlates that are associated with clinical response or resistance to the triple combination. Biomarker analyses will include study of pre-treatment and on-treatment biopsies as well as analyses of select serum and PBMC markers.

3. Investigational Plan

3.1 Study Design and Duration

This study is a Phase 1/1b, open-label, single institution, dose escalation and dose expansion study to evaluate the efficacy, safety, and tolerability of APX005M in combination with nivolumab and cabiralizumab in patients with advanced melanoma, NSCLC, and RCC.

Nivolumab is a fully human monoclonal antibody directed against PD-1. Cabiralizumab is a humanized monoclonal antibody directed against CSF1R. APX005M is a humanized IgG1 agonistic monoclonal antibody that binds CD40.

Patients will be sequentially enrolled in the phase 1 dose escalation portion in 6 cohorts using a standard 3 + 3 design to determine safety, characterize the adverse events, and establish the MTD of APX005M in combination with cabiralizumab and nivolumab. A minimum of 48 hours observation will be required after each patient is enrolled in cohorts 1-6, before a subsequent patient can be enrolled. Approximately 3 patients will be enrolled into each cohort. Cohorts 1, 3, and 5 will include cabiralizumab at the fixed RP2D of 4 mg/kg and dose escalation of APX005M. Cohorts 2, 4, and 6 will include nivolumab at 240 mg, cabiralizumab at 4 mg/kg, and dose escalation of APX005M.

All study drugs will be given on Day 1 of each 14-day treatment cycle. Pre-medications will be given before nivolumab. Nivolumab will be administered as an IV infusion over 30 minutes first followed by a 30-minute break and then cabiralizumab will be administered as an IV infusion over 30 minutes. After another 30-minute break, APX005M will be administered as an IV infusion over 60 minutes. Patients must remain near the vicinity of a hospital with rapid access to an intensive care unit setting during the initial 48 hour period after treatment for the first two treatment cycles.

Dose escalation will be based on the number of DLTs experienced during the DLT evaluation interval as determined by the PI and Industry Collaborators (see Section 3.1.2.1.1 for DLT criteria). The DLT evaluation interval begins on the first day of treatment and continues for 28 days.

The phase 1b portion will enroll patients in three cohorts (advanced melanoma, NSCLC, and RCC) to study the RP2D of APX005M in combination with nivolumab and cabiralizumab.

3.1.1 Screening Period

All screening evaluations must be completed and reviewed by the Investigator for the enrollment process to confirm that patients meet all eligibility criteria before the first infusion of study drug. Written informed consent for participation in the study must be obtained before performing any study specific screening tests or procedures. Screening assessments will be performed within 28 days prior to the first dose of study drug unless otherwise specified.

The Investigator may repeat qualifying lab tests and vitals/ECGs prior to enrollment if a non-qualifying finding is considered an error or an acute finding is likely to meet eligibility criteria upon repeat testing.

Study procedure-related AEs that occur after signing of the ICF and before administration of the first study drug dose will be collected during this period.

3.1.2 Treatment Period

3.1.2.1 Phase 1 Cohorts and Combination Dose Escalation Cohorts

Phase 1 consists of three dose escalation cohorts of APX005M in combination with cabiralizumab alone, and three dose-escalation cohorts of APX005M in combination with nivolumab and cabiralizumab. A minimum of 3 patients will be enrolled in each cohort. The planned dose levels and schedules for the Phase 1 dose escalation cohorts are as follows in Table 2:

[figure not shown]
Table 2

Cohort	Nivolumab (mg)	Cabiralizumab (mg/kg)	APX005M (mg/kg)
1	Not given	4	0.03
2	240	4	0.03
3	Not given	4	0.1
4	240	4	0.1
5	Not given	4	0.3
6	240	4	0.3

A minimum of 48 hours observation will be required after each patient is enrolled in cohorts 1-6, before a subsequent patient can be enrolled. As depicted in Figure 6, accrual to cohorts 2 and 3 will only start after the last patient in cohort 1 has been observed for toxicity for at least two 14-day cycles (28 days in total); accrual to cohort 4 will commence when the last patients on cohorts

2 and 3 have been observed for at least two 14-day cycles, accrual to cohort 5 will commence only after the last patient on cohort 3 has been observed for at least two 14 day cycles, and accrual to cohort 6 will accrue once the last patients on cohorts 4 and 5 have been observed for at least two 14-day cycles. Doses will be de-escalated as determined by toxicities.

Figure 6

All dose escalation decisions will be based on assessment of toxicity, overall safety, and tolerability. Dose escalation decisions will be agreed upon by the PIs and study collaborators. Prior to initiating each new dose level or expanding an existing dose level, a safety teleconference will be held wherein the PIs and study collaborators will review patient data, including but not limited to the available demographics, dosing, concomitant medications, hematology, serum chemistry, and AEs; and confer and document agreement that dose escalation or expanding an existing dose level is considered appropriate. If the PIs collectively agree, following review of safety, PK, and PD data (if available), that a different dose escalation scheme should be used than the one outlined, this will be permitted. Review of safety, PK, and PD profiles may inform decisions to add cohorts with alternative dose levels or dose regimens (e.g., less frequent dosing) in order to reach an optimal target exposure.

For the purpose of dose escalation, we will require a 28 day observation period from the time the last patient in a given cohort was treated. For the purpose of calculating the MTD, we will require a minimum of 28 days of observation for each patient.

Dose escalation in Phase 1 will proceed as follows:

If none of the first 3 evaluable patients in a dose cohort experience a DLT in the first two cycles, then the next 3 patients will be treated at the next higher dose cohort. If 1 of 3 patients within a cohort experiences a DLT in the first two cycles, then 3 additional patients will be added to that cohort. If a second patient experiences a DLT at that dose level in the first two cycles, the next cohort will not be initiated, and the dose of one or more drugs will be de-escalated. Patients at each dose level will be evaluated for at least 28 days from the start of treatment before additional patients can be treated at a higher dose level. If DLTs are observed in 2 or more patients within a cohort, the maximum tolerated dose (MTD) will have been exceeded and no further patients will be treated at that dose level.

DLT evaluation and enrollment decisions will follow the guidance in Table 3.

Table 3: Algorithm for Dose-Escalation Decisions

Number of Patients with DLT at a Given Dose Level	Dose Escalation Decision Rule
0/3	Escalation will occur into the next highest dose cohort
1/3	Enroll 3 additional patients at current dose level
$\geq 2/3$	Stop enrollment. Enroll 3 more patients at the lower dose level, if only 3 were previously entered, or at an intermediate dose level.
1/6	Open next cohort
$\geq 2/6$	Stop enrollment. Enter 3 more patients at the lower dose level at an intermediate dose level.

Dose escalation will continue until either the MTD or maximum planned dose of APX005M is reached, with a minimum of 3 patients enrolled in each cohort.

The MTD is defined as the highest dose associated with DLTs in less than or equal to 33% of patients receiving APX005M in combination with cabiralizumab or with cabiralizumab and nivolumab, administered during the DLT period. This will normally be the dose recommended for further study; however, based on review of safety, PK, and PD (if available) data, the RP2D could be lower than the MTD. If the MTD is not reached, and the highest evaluated APX005M dose in combination with cabiralizumab and nivolumab is well tolerated, the data will be reviewed to assess whether further dose escalations of APX005M are warranted.

In order to calculate the MTD and RP2D, every patient included in this calculation must have received at least 2 doses of study drugs and have been monitored for at least 2 full cycles (28 days). If a patient does not receive 2 doses of study drugs and does not complete safety assessments (e.g., safety lab and/or AE reporting) in the first 28 days for reasons other than drug-

related AEs (e.g., disease progression or withdrawal of consent), then an additional patient will be enrolled into the cohort so that the cohort has at least 3 patients evaluable for 28 days. All such discussions and decisions will be documented as part of the dose escalation decision-making process.

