4.3 Method of Assigning Patient Identification

Patients must be able to provide written informed consent and meet all eligibility criteria. No waivers of inclusion or exclusion criteria will be granted by Sponsor or its designee for any patient enrolled in the study. Before enrolling a patient, all eligibility criteria must be satisfied.

See Section 4.4.1 and Figure 6 for dosing schema. Patients who qualify for Phase 1 dose escalation of the study will be enrolled as follows:

- Cohort 1 will be enrolled first and these patients will be followed one 14-day cycle.
- Once the DLT follow-up period of 28 days is cleared for Cohort 1, simultaneous enrollment to Cohort 2 and Cohort 3 will occur. Patients in these cohorts will be treated for a total of one 14-day cycle.
- Simultaneous enrollment into Cohort 4 and Cohort 5 will proceed once the 14-day DLT

period for dose escalation is cleared in the preceeding Cohorts 2 and 3.

- Once the DLT period of 28 days for dose escalation is cleared Cohorts 4 and 5, enrollment to the final Cohort 6 will occur.
- The MTD will be calculated for patients who have received at least 2 cycles (at least 28 days) of study drug.
- Dose escalation into sequential dose levels of APX005M in combination with cabiralizumab and nivolumab may proceed until DLTs are observed either in the cabiralizumab/APX005M doublet therapy cohorts 1, 3, and 5 or in the nivolumab/cabiralizumab/APX005M triplet therapy cohorts after discussion and agreement between the PIs and Industry Collaborators.

In Phase 1b, a maximum of 34 patients will be enrolled per disease-specific cohort (advanced melanoma, NSCLC, or RCC). Enrollment will be open for all cohorts in parallel and will continue until the enrollment target is reached. Once a disease cohort is filled, further enrollment will be restricted to the cohort(s) that have not been filled. A total of approximately 102 patients will be enrolled in the Phase 1b arm of the study.

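### Sections 3.1.2.1 and 4.3 set different gates for Cohort 5: Cohort 3 alone in one, both Cohorts 2 and 3 in the other

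*Combined protocol and SAP*

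**What the plan says.** Phase 1 alternates doublet cohorts (1, 3, 5: cabiralizumab and APX005M) with triplet cohorts (2, 4, 6: the same with nivolumab). Cohort 5 is the doublet at APX005M 0.3 mg/kg, the highest planned dose.

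Section 3.1.2.1 sets the gates in one sentence. For Cohort 4, the condition covers the final patient in each of two cohorts: "2 and 3 have been observed for at least two 14-day cycles". For the next doublet step, "accrual to cohort 5 will commence only after the last patient on cohort 3 has been observed for at least two 14 day cycles". For the last step, "accrual to cohort 6 will accrue once the last patients on cohorts 4 and 5 have been observed", again over two cycles. Two predecessors are named for Cohorts 4 and 6, and one for Cohort 5. Table 3 in the same section counts DLTs cohort by cohort. Escalation follows 0/3, a cohort with 1/3 expands to six, two or more DLTs stop it, and the entry for 1/6 is "Open next cohort".

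Section 4.3 describes the same step differently. Its sentence begins "Simultaneous enrollment into Cohort 4 and Cohort 5 will proceed once the 14-day DLT" and, across a page break, names the cohorts concerned: "period for dose escalation is cleared in the preceeding Cohorts 2 and 3". A later bullet, which is subject to the PIs and the industry collaborators agreeing, says that triplet escalation "may proceed until DLTs are observed either in the cabiralizumab/APX005M doublet therapy cohorts 1, 3, and 5 or in the nivolumab/cabiralizumab/APX005M triplet therapy cohorts". The synopsis also says that Cohorts 4 and 5 run at the same time.

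**The concern.** A 3+3 design with two interleaved regimens needs one unambiguous predecessor list per cohort. Here the lists for Cohort 5 differ by one cohort, and that cohort is the triplet. Under Section 3.1.2.1, nothing tells the reader that a failed or unresolved Cohort 2 holds back Cohort 5. Under Section 4.3 it does. The same data can therefore lead one reader to start treating patients at the highest planned APX005M dose and another to hold. Safety and dose finding are the phase 1 primary objectives, and Cohort 5 is itself a gate for Cohort 6.

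**Working it through.** There is no stated figure to reproduce; the conflict is one of rules. The check has three steps.

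**1. Outcomes on which the gates disagree.** Under Table 3 a cohort ends as 0/3 or 1/6 (clears), or as ≥2/3 or ≥2/6 (fails). Cohorts 2 and 3 together give 4 × 4 = 16 outcome pairs. I read *observed* in Section 3.1.2.1 as *cleared under Table 3*.

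- Cohort 4: both sections require Cohorts 2 and 3. They agree in 16 of 16 pairs.
- Cohort 5: Section 3.1.2.1 requires Cohort 3; Section 4.3 requires Cohorts 2 and 3. They disagree in 4 of 16 pairs, namely Cohort 2 failing (two ways) with Cohort 3 clearing (two ways).

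**2. How likely those outcomes are.** For a true DLT rate p, the chance that a cohort clears is

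pass(p) = (1−p)³ + 3p(1−p)⁵

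For example, pass(0.10) = 0.729 + 0.177 = 0.906 and pass(0.20) = 0.512 + 0.197 = 0.709. With independent cohorts, the chance of disagreement is [1 − pass(p₂)] × pass(p₃). Section 1.2 notes that APX005M and cabiralizumab have not been combined before, and the documents give no DLT rate for either regimen. The rates below are therefore assumptions.

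| Assumed rate, Cohort 2 / Cohort 3 | Cohort 2 fails | Cohort 3 clears | Gates disagree |
|---|---|---|---|
| 5% / 5% | 0.0266 | 0.9734 | 2.6% |
| 10% / 20% | 0.0939 | 0.7086 | 6.7% |
| 10% / 10% | 0.0939 | 0.9061 | 8.5% |
| 20% / 10% | 0.2914 | 0.9061 | 26% |
| 30% / 20% | 0.5057 | 0.7086 | 36% |
| 40% / 20% | 0.6907 | 0.7086 | 49% |

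**3. Cohort 2 not yet resolved.** The sections can also diverge before any failure. Cohort 2 must expand after exactly one DLT in three with probability 3p(1−p)², which is 24%, 38% and 44% at p = 10%, 20% and 30%. If Cohort 3 clears meanwhile, Section 3.1.2.1 lets Cohort 5 start while Cohort 2 is still enrolling; Section 4.3 does not. These figures overlap with the table, since some expansions end in failure, and must not be added to it.

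**What follows downstream.** When Cohort 2 fails, Cohort 4 stays closed under both sections. Cohort 6 needs Cohort 4, so it stays closed too. The disagreement is confined to Cohort 5.

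**The case against.** The strongest reply is that neither section is a mechanical rule. Section 3.1.2.1 sets an observation time for Cohort 3 and does not state that a failed Cohort 2 leaves Cohort 5 free to open. It bases every escalation decision on toxicity, safety and tolerability, requires a documented safety teleconference before each new dose level, and lets the PIs agree a different scheme. Figure 6 might settle the matter but was not available in the text reviewed. This softens the conflict without removing it. A clause that permits departure from the outlined scheme presupposes a single outlined scheme, and the teleconference still needs to know which default it is applying.

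A second reply concerns size. The larger figures assume that Cohort 2, at APX005M 0.03 mg/kg, is more toxic than Cohort 3 at 0.1 mg/kg. Section 1.3.6.3.2 reports exposure at 0.03 mg/kg or less as mostly below quantitation, and Section 1.3.6.3.3 reports one DLT in six at 1 mg/kg as a single agent. Low rates are therefore plausible, and the low end of the table deserves equal weight.

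Three stronger readings are tempting and are not supported:

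- *Any single DLT stops escalation under Section 4.3.* The bullet gives no count, is about the triplet, says that escalation may proceed, and is qualified by discussion and agreement. A literal conflict with the 1/6 row of Table 3 is one reading of a loose summary sentence, not a stated rule.
- *The regimens hold each other back under one section and not under the other.* The difference runs one way only, from triplet Cohort 2 to doublet Cohort 5. Section 3.1.2.1 already gates Cohort 4 on Cohort 3 and Cohort 6 on Cohort 5.
- *The triplet MTD carried into phase 1b changes.* When Cohort 2 fails and Cohort 3 clears, the planned triplet path is the same under both sections.

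**Conclusion.** The conflict stands, in a narrow form: the gate for Cohort 5 is Cohort 3 alone in Section 3.1.2.1 and Cohorts 2 and 3 together in Section 4.3. It matters when Cohort 2 fails or is unresolved and Cohort 3 clears. The chance of the failing case ranges from 2.6% to 49% over the rates shown, and that range rests on assumed DLT rates, independent cohorts and clearance as defined in Table 3. What depends on the choice is how many patients are treated in Cohort 5 and any MTD for the doublet. The missing count in the DLT bullet of Section 4.3 is a secondary drafting point. The matter is an internal inconsistency in a safety rule and should be corrected.

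**What to change.** Reconcile the passages. State one gate for each cohort in Section 3.1.2.1 and Figure 6, and say explicitly whether a failed Cohort 2, or one still expanding after 1/3, holds back Cohort 5. Make Section 4.3 and the synopsis refer to that statement instead of restating it. Tie the DLT wording in Section 4.3 to one stated counting rule, so that it can be read consistently with the 1/6 row of Table 3. The same sentence of Section 4.3 uses a 14-day DLT period where Section 3.1.2.1 uses 28 days; that separate discrepancy can be settled in the same edit. This review does not choose the gate or the rule.

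The cost is protocol wording only. If escalation is already complete, which the documents do not say, the sponsor should record which gate was applied.
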